Postmarket Outcomes Study for Evaluation of the Superion Spacer

PRESS 2

A4086

CLINICAL INVESTIGATION PLAN

Sponsored By

Boston Scientific Neuromodulation Corporation
[name]
[name]
United States of America

This protocol contains confidential information for use by the Investigators and their designated representatives participating in this clinical investigation. The protocol should be held confidential and maintained in a secure location.

Do not copy or distribute without written permission from the Sponsor.

Contact Information

Role	Contact

Original Release: 24 Jun 2020

Current Version: 02Mar2022

[REDACTED]	[REDACTED]	[REDACTED]	[REDACTED]	[REDACTED]	[REDACTED]
[REDACTED]	[REDACTED]	[REDACTED]	[REDACTED]	[REDACTED]	[REDACTED]
[REDACTED]	[REDACTED]	[REDACTED]	[REDACTED]	[REDACTED]	[REDACTED]
[REDACTED]	[REDACTED]	[REDACTED]	[REDACTED]	[REDACTED]	[REDACTED]
[REDACTED]	[REDACTED]	[REDACTED]	[REDACTED]	[REDACTED]	[REDACTED]

Confidential

2. Protocol Synopsis

Postmarket Outcomes Study for Evaluation of the Superion Spacer PRESS 2	
Study Objective(s)	To compile real-world outcomes for Boston Scientific commercially approved Indirect Decompression Systems (IDS) in routine clinical practice, when used according to the applicable Instructions for Use.
Indication(s) for Use	
The Superion® Indirect Decompression System (IDS) is intended to treat skeletally mature patients suffering from pain, numbness, and/or cramping in the legs (neurogenic intermittent claudication) secondary to a diagnosis of moderate degenerative lumbar spinal stenosis, with or without Grade 1 spondylolisthesis, confirmed by X-ray, MRI and/or CT evidence of thickened ligamentum flavum, narrowed lateral recess, and/or central canal or foraminal narrowing. The Superion IDS is indicated for those patients with impaired physical function who experience relief in flexion from symptoms of leg/buttock/groin pain, numbness, and/or cramping, with or without back pain. The Superion IDS may be implanted at one or two adjacent lumbar levels in patients in whom treatment is indicated at no more than two levels, from L1 to L5.
 
For this intended use, moderate degenerative lumbar spinal stenosis is defined as follows:
 
 • 25% to 50% reduction in the central canal and/or nerve root canal (subarticular, neuroforaminal) compared to the adjacent levels on radiographic studies, with radiographic confirmation of any one of the following: 
 ○ Evidence of thecal sac and/or cauda equina compression ○ Evidence of nerve root impingement (displacement or compression) by either osseous or non-osseous elements ○ Evidence of hypertrophic facets with canal encroachment • AND Associated with the following clinical signs: 
 ○ Presents with moderately impaired Physical Function (PF) defined as a score of ≥ 2.0 of the Zurich Claudication Questionnaire (ZCQ) ○ Ability to sit for 50 minutes without pain and to walk 50 feet or more.

Postmarket Outcomes Study for Evaluation of the Superion Spacer
PRESS 2

Commercial Device/System	Superion® IDS device
Study Design	Prospective, multi-center, global outcomes study
Clinical Endpoints	
The following clinical endpoints will be included in this registry. Study assessments used to derive each endpoint are denoted in parenthesis.
 
• Proportion of subjects with an improvement of 20 mm for low back pain at 3 months, 6 months, 1 year, 2 years, and 3 years post-procedure compared with Baseline (VAS)• Proportion of subjects with an improvement of 20 mm for leg pain at 3 months, 6 months, 1 year, 2 years, and 3 years post-procedure compared with Baseline (VAS)

Postmarket Outcomes Study for Evaluation of the Superion Spacer PRESS 2

	
 Percent Pain Relief at 3 months, 6 months, 1 year, 2 years and 3 years post-procedure compared with Baseline (PPR) Change in overall quality of life at 3 months, 6 months, 1 year, 2 years and 3 years post-procedure compared with Baseline (EQ-5D-5L)
Safety Parameters	Rates of occurrence of all device hardware and/or procedure related non-serious adverse events, all serious adverse events, and unanticipated adverse events through the end of the study.

Postmarket Outcomes Study for Evaluation of the Superion Spacer
PRESS 2

Follow-up Schedule	
Study events occur at the following time points for subjects:
 
• Screening Period• Baseline (up to 30 days post Informed Consent)• Surgical Procedure (up to 90 days post Baseline Visit)• 3-Month visit (90 days \pm 45 days post procedure)• 6-Month visit (180 days \pm 60 days post-procedure)• 1-Year Visit (365 days \pm 60 days post-procedure)• 2-Year Visit (730 days \pm 60 days post-procedure)• 3-Year Visit (1,095 days \pm 60 days post-procedure) 
The above study events will occur for previously enrolled PRESS subjects as applicable (i.e. to be completed study timepoints).

Inclusion Criteria	
IC1. Scheduled to receive or previously received a commercially approved Boston Scientific Indirect Decompression System, per local Instructions for Use (IFU)
 
IC2. Signed a valid, IRB approved informed consent form

Exclusion Criteria	
EC1. Meets any contraindication in BSC Indirect Decompression Systems local IFU

Statistical Methods	

Postmarket Outcomes Study for Evaluation of the Superion Spacer
PRESS 2

Primary Statistical Hypothesis	Descriptive statistics will be utilized to report the clinical endpoints and their changes from baseline at 3 months, 6 months, 1 year, 2 years, and 3 years post-procedure
Statistical Test Method	NA
Sample Size Parameters	NA

[figure not shown]
[figure not shown]
Confidential

3. 

Confidential

Confidential

Confidential

4. *Introduction*

4.1. *Background*

Lumbar Spinal Stenosis (LSS) is characterized as a narrowing of the spinal canal and/or the intervertebral foramina that decreases space for the neural elements in the lumbar region of the spine.¹⁻⁶ As early as the 1950's it was recognized by Verbiest⁷ that structural narrowing of the vertebral canal could compress the *cauda equina* and produce neurogenic claudication symptoms. These include leg pain (and occasionally cramping, numbness, or weakness) on walking or standing which is relieved by sitting or spinal flexion.

Indirect Compression Systems (IDS) are an option in well-selected patients with impaired physical function who experience relief in flexion from symptoms of leg/buttock/groin pain, numbness, and/or cramping, with or without back pain, and who have undergone at least 6 months of non-operative treatment. Additionally, IDS offer significant overall improvement in health-related quality of life with the most improvement in areas of physical functioning⁸.

The Superion Indirect Decompression System (IDS) was granted FDA approval in the U.S. in 2015. The Superion IDS is a minimally invasive spinal implant that treats LSS symptoms by limiting extension at the symptomatic level that compresses the neural elements and is designed for percutaneous surgical placement.

4.2. *Study Rationale*

The purpose of this outcomes study is to gather evidence documenting the clinical outcomes associated with treatment of moderate degenerative lumbar spinal stenosis using the Superion Indirect Decompression System (IDS).

5. (Commercial) Device Description (part of Standard of Care)

5.1. *Commercial Device Description*

The Superion® Indirect Decompression System (IDS) indicated to treat skeletally mature patients suffering from pain, numbness, and/or cramping in the legs (neurogenic intermittent claudication) secondary to a diagnosis of moderate lumbar spinal stenosis, with or without Grade 1 spondylolisthesis, confirmed by X-ray, MRI and/or CT evidence of thickened ligamentum flavum, narrowed lateral recess, and/or central canal or foraminal narrowing.

The Superion Indirect Decompression System (IDS) (Superion implant) is approved by the Food and Drug Administration (FDA) and will be used per approved Instructions for Use (IFU) in this study.

Figure 5-1: Superion Indirect Compression System

6. Study Objectives and Endpoints

6.1. *Study Objectives*

[figure not shown]
[figure not shown]
The primary objective of this study is to compile real-world outcomes for Boston Scientific commercially approved Indirect Decompression Systems (IDS) in routine clinical practice, when used according to the applicable Instructions for Use.

6.2. *Clinical Endpoints*

The following clinical endpoints will be included in this registry. Study assessments used to derive each endpoint is denoted in parenthesis:

- Proportion of subjects with an improvement of 20 mm for low back pain at 3 months, 6 months, 1 year, 2 years and 3 years post-procedure compared with Baseline (VAS)
- Proportion of subjects with an improvement of 20 mm for leg pain at 3 months, 6 months, 1 year, 2 years and 3 years post-procedure compared with Baseline (VAS)
- [REDACTED]
- [REDACTED]
- [REDACTED]

Confidential

- Percent Pain Relief at 3 months, 6 months, 1 year, 2 years and 3 years post-procedure compared with Baseline (PPR)

- 

- 

- Change in overall quality of life at 3 months, 6 months, 1 year, 2 years and 3 years post-procedure compared with Baseline (EQ-5D-5L)

- 

- 

[figure not shown]
- 

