A subject is considered lost-to-follow-up after 3 unsuccessful contact attempts have been made to reach the subject (including those who relocate but cannot be transferred to another participating site). Staff at the participating site should make a good faith effort to contact the subject with three documented communication attempts, at least one of which must be in writing, sent via a traceable method.

Data collected up to the point of subject withdrawal or lost to follow-up may be used for study analysis in accordance with applicable regulations.

Withdrawn subjects will be followed per the End of Study Action Plan as described below.

9.3. *Subject Status and Classification*

Subjects are considered enrolled in the study at the time written informed consent is provided. Subjects who sign the informed consent form but do not meet all study eligibility criteria (i.e., screen failure), or withdraw prior to completion of the Baseline Visit, will not be implanted. Subjects that are enrolled but not implanted will be deemed as “enrolled” and their reason for ineligibility or withdrawal prior to implant will be documented.

The overall enrollment in the study will be capped to yield up to 3,000 subjects with an IDS implant. Per site enrollment will be capped initially at 30 newly implanted subjects. The initial cap can be increased based upon written communication of sponsor approval.

The study will implement an *Enrollment Communication Plan*. The plan will outline the specific activities, as well as the nature and timing of communications to investigators in order to minimize the risk of enrollment beyond the protocol-specified enrollment caps.

[figure not shown]
9.4. *End-of-Study Definition*

A clinical trial is considered completed when the last participant’s last study visit has occurred. Upon end of study, subjects will be followed per standard of care.

10. Study Methods

10.1. *Data Collection*

The data collection schedules are shown in tables 10.1-1 (newly enrolled subjects) and 10.1-2 (previously enrolled/implanted subjects (under PRESS).

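### Do the overlapping 3-month and 6-month visit windows leave an assessment on days 120 to 135 without a clear time point?

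*Combined protocol and SAP*

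**What the plan says.** The Follow-up Schedule in the Protocol Synopsis (section 2) lists five post-procedure visits, each with a target day and a tolerance. The first is given as "3-Month visit (90 days \pm 45 days post procedure". The second has a wider tolerance and is given as "6-Month visit (180 days \pm 60 days post-procedure". The three later visits have targets of 365, 730 and 1,095 days, and each may fall up to 60 days either side of its target.

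For subjects who come over from the earlier PRESS registry, it adds: "The above study events will occur for previously enrolled PRESS subjects as applicable (i.e. to be completed study timepoints".

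The Statistical Methods rows of the synopsis state: "Descriptive statistics will be utilized to report the clinical endpoints and their changes from baseline at 3 months, 6 months", and then name the three later time points. The entries for test method and sample size are both marked not applicable.

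Section 10.1 says: "The data collection schedules are shown in tables 10.1-1 (newly enrolled subjects) and 10.1-2". It assigns the second of these tables to subjects previously enrolled or implanted under PRESS. Both tables are blacked out in the public copy. Section 12.3 (Study Assessments) shows only its heading, and sections 11 and 12.1 do not appear.

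**The concern.** The clinical endpoints (VAS responder proportions for back and leg pain, percent pain relief, EQ-5D-5L) are reported separately at 3 and at 6 months. If two windows share days, one assessment can satisfy both. The windows alone would even accept a 6-month visit on day 120 and a 3-month visit on day 135.

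The case that seems open is a subject seen only once between days 45 and 240, on one of the shared days. Calling that visit 3 months leaves 6 months missing, and the reverse. The choice moves the subject between the denominators of the two time points. If it were made after the data were seen, it could in principle be made to suit the result. A PRESS subject who transfers on those days without a 3-month assessment looks like a natural example, since both time points would still be open.

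**Working it through.** **Inputs.** Target days and tolerances are from the synopsis Follow-up Schedule. The plan does not print the end days, so there is no stated figure to reproduce.

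**Windows.** Window = [target − tolerance, target + tolerance].

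| Visit | Calculation | Days |
|---|---|---|
| 3 months | 90 ± 45 | 45 to 135 |
| 6 months | 180 ± 60 | 120 to 240 |
| 1 year | 365 ± 60 | 305 to 425 |
| 2 years | 730 ± 60 | 670 to 790 |
| 3 years | 1,095 ± 60 | 1,035 to 1,155 |

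**Adjacent pairs.** Start of the later window minus end of the earlier one:

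- 3 and 6 months: 120 − 135 = −15, an overlap of 135 − 120 + 1 = 16 days
- 6 months and 1 year: 305 − 240 = 65, no overlap
- 1 and 2 years: 670 − 425 = 245, no overlap
- 2 and 3 years: 1,035 − 790 = 245, no overlap

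The 3-month window has 135 − 45 + 1 = 91 days and the 6-month window 240 − 120 + 1 = 121. The overlap is 16/91 = 17.6% of the first and 16/121 = 13.2% of the second. These are shares of calendar days, not of visits. Visits should cluster near their targets, and the documents give no data on timing.

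**What happens under the plan.** Assume each assessment is recorded under the visit at which it was collected.

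1. Both visits done: there are two records with two labels, and each counts once.
2. One visit done, on a shared day: it counts under its label, and the other time point is missing. Either label is in window, so neither is a deviation.

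No assessment counts twice and none is left without a place.

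**Size for a responder proportion.** Suppose that at one time point a fraction f of the assessed subjects are lone cases that could have carried the other label. Let p₁ be the response rate among them and p₀ the rate among the rest. The proportion with them is (1 − f)p₀ + f·p₁, and without them it is p₀. The difference is f(p₁ − p₀), which cannot exceed f in size. The documents do not give f.

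**Would sorting by nearest target be better?** The midpoint of the targets is (90 + 180)/2 = 135. Days 120 to 134 are nearer to day 90 (day 134: 44 against 46 days), and day 135 is a tie (45 against 45). Take a lone 6-month visit on day 125: it is 35 days from the first target and 55 from the second, so a nearest-target rule for lone assessments would make it a 3-month visit. The synopsis accepts day 125 as a valid 6-month day. The same visit would stay at 6 months had the subject also attended at 3 months. Assignment would then depend on whether another visit is missing, which the visit label avoids.

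**The case for a change.** The strongest case for acting is that the overlap is real and stands in current text, that the label of a lone visit rests on the site's choice, and that both choices pass a window check. One sentence fixed before the data are summarised would cost almost nothing and would remove any appearance of choosing afterwards.

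The arithmetic stands in full. It also stands that the visible text does not say in so many words that summaries go by visit label.

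The rest carries less weight. A label that is good enough when a second visit exists is equally good when it is the only one. The transferring PRESS subject is a weak example, because section 10.1 assigns a schedule table to exactly that group and the table is redacted. A gap left by redaction is not a gap in the plan. A percentage of affected visits could be computed only by assuming a spread of visit days. It would count every visit in the overlap, not the much narrower set of subjects with no other assessment in either window.

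**Conclusion.** The overlap of 16 days is correctly calculated and is the only one in the schedule, but it is not an error. Overlapping tolerances for separately named visits are a fair trade-off in an outcomes study run in routine practice, where wide windows keep visits in the data. An analyst who tabulates by collected visit, counting each assessment once, fills the remaining detail sensibly. Re-sorting by day would bring no gain and would make assignment depend on missingness elsewhere.

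The effect is confined to subjects with a single assessment between days 45 and 240 that falls on days 120 to 135. It concerns descriptive summaries at two of five time points and touches no test, error rate or sample size. The number of such subjects cannot be derived from the documents.

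This rests on one assumption: that assessments are recorded under a named visit and summarised that way. The synopsis, which lists the windows as timing for named study events, supports this reading. A colleague with the unredacted plan can confirm it in one look at section 10.1 and the analysis text. The plan needs no change on this point.

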6.3. Safety Parameters

Rates of occurrence of all device hardware and/or procedure-related non-serious adverse events, all serious adverse events, and unanticipated adverse events through the end of the study.

7. Study Design

8.2. Inclusion Criteria

Subjects who meet all of the following criteria (see Table 8.2-1) may be given consideration for inclusion in this clinical investigation, provided no exclusion criterion (see Section 8.3) is met.

Table 8.2-1: Inclusion Criteria

Inclusion Criteria	IC3. Scheduled to receive or previously received a commercially approved Boston Scientific Indirect Decompression System, per local Instructions for Use (IFU) IC4. Signed a valid, IRB approved informed consent form
---------------------------	---

8.3. Exclusion Criteria

Subjects who meet any one of the following criteria cannot be included in this study or will be excluded from this clinical study.

Table 8.3-1: Exclusion Criteria

Exclusion Criteria	EC1. Meets any contraindication in BSC Indirect Decompression Systems local IFUCurrently diagnosed with a cognitive impairment, or exhibits any characteristic, that would limit the ability to assess pain relief or to complete study assessments in the opinion of the investigator
---------------------------	--

9. Subject Accountability

9.1. *Point of Enrollment*

A subject will be considered enrolled in the study when the Informed Consent Form (ICF) is signed. A subject will be considered implanted when a Superion IDS is successfully implanted.

9.2. *Withdrawal*

All subjects enrolled in the clinical study (including those withdrawn from the clinical study or lost to follow-up) shall be accounted for and documented. If a subject is withdrawn from the clinical investigation, the reason(s) shall be reported. If such withdrawal is due to problems related to investigational device safety or performance, the investigator shall ask for the subject's permission to follow his/her status/condition outside of the clinical study.

While study withdrawal is discouraged, subjects may withdraw from the study at any time, with or without reason and without prejudice to further treatment. In all cases of withdrawal or discontinuation, the Investigator will make all reasonable efforts to determine the reason for the subject's withdrawal. Subjects may be discontinued from the study for various reasons, which may include:

- Withdrawal of consent
- A safety concern defined by the Principal Investigator and/or Boston Scientific Neuromodulation (e.g., adverse event)
- Study non-compliance
- Inadequate use of device that may impact study outcomes
- Subject did not meet inclusion criteria or met an exclusion criterion after signing informed consent
- Surgical intervention that affects the Superion Indirect Decompression System
- Lost to follow-up
- Death of the subject

If device implantation is unsuccessful, the subject will be followed for 2 weeks post-implantation attempt to assess for procedure related adverse events. If Superion IDS is explanted, the subject should be followed for 30 days post-explant to assess for related adverse events and withdrawn. Subjects that undergo a revision or replacement procedure may continue in the study.

A subject is considered lost-to-follow-up after 3 unsuccessful contact attempts have been made to reach the subject (including those who relocate but cannot be transferred to another participating site). Staff at the participating site should make a good faith effort to contact the subject with three documented communication attempts, at least one of which must be in writing, sent via a traceable method.

Data collected up to the point of subject withdrawal or lost to follow-up may be used for study analysis in accordance with applicable regulations.

Withdrawn subjects will be followed per the End of Study Action Plan as described below.

9.3. *Subject Status and Classification*

Subjects are considered enrolled in the study at the time written informed consent is provided. Subjects who sign the informed consent form but do not meet all study eligibility criteria (i.e., screen failure), or withdraw prior to completion of the Baseline Visit, will not be implanted. Subjects that are enrolled but not implanted will be deemed as “enrolled” and their reason for ineligibility or withdrawal prior to implant will be documented.

The overall enrollment in the study will be capped to yield up to 3,000 subjects with an IDS implant. Per site enrollment will be capped initially at 30 newly implanted subjects. The initial cap can be increased based upon written communication of sponsor approval.

The study will implement an *Enrollment Communication Plan*. The plan will outline the specific activities, as well as the nature and timing of communications to investigators in order to minimize the risk of enrollment beyond the protocol-specified enrollment caps.

[figure not shown]
9.4. *End-of-Study Definition*

A clinical trial is considered completed when the last participant’s last study visit has occurred. Upon end of study, subjects will be followed per standard of care.

10. Study Methods

10.1. *Data Collection*

The data collection schedules are shown in tables 10.1-1 (newly enrolled subjects) and 10.1-2 (previously enrolled/implanted subjects (under PRESS).

A large table with 12 rows and 10 columns. The first column contains blacked-out names. The second column has a blacked-out name in the first row, a red arrow pointing right in the second row, and blacked-out names in the remaining rows. The third column has blacked-out names in the first four rows, then a red arrow pointing right in the fifth row, and blacked-out names in the remaining rows. The fourth column has blacked-out names in the first four rows, then a red arrow pointing right in the fifth row, and blacked-out names in the remaining rows. The fifth through tenth columns each have blacked-out names in every row.

[REDACTED]									
[REDACTED]									
[REDACTED]									
[REDACTED]									
[REDACTED]									
[REDACTED]									
[REDACTED]									
[REDACTED]									
[REDACTED]									
[REDACTED]									
[REDACTED]									
[REDACTED]									
[REDACTED]									

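### Section 9.2 withdraws explanted subjects after 30 days, so an observed-case 20 mm responder rate would largely describe subjects who kept the device; report the explant count and a non-responder sensitivity rate beside it

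*Combined protocol and SAP*

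**What the plan says.** Section 9.2 (Withdrawal) sets the rule for device removal: "If Superion IDS is explanted, the subject should be followed for 30 days post-explant to assess for related adverse events and withdrawn". The stated purpose of the 30 days is adverse events. The next sentence treats other re-operations differently: "Subjects that undergo a revision or replacement procedure may continue in the study". On use of data, the same section says: "Data collected up to the point of subject withdrawal or lost to follow-up may be used for study analysis in accordance with applicable regulations".

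Two sentences in Section 9.2 point to some further follow-up. When withdrawal is for device safety or performance, the investigator asks for "permission to follow his/her status/condition outside of the clinical study". And: "Withdrawn subjects will be followed per the End of Study Action Plan as described below". The content of that plan does not appear in the visible text.

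The objective in Section 6.1 is "to compile real-world outcomes for Boston Scientific commercially approved Indirect Decompression Systems (IDS) in routine clinical practice", when the device is used according to its Instructions for Use. Section 6.2 gives the leg-pain endpoint as "Proportion of subjects with an improvement of 20 mm for leg pain at 3 months, 6 months, 1 year, 2 years and 3 years", measured by VAS against Baseline, with a matching endpoint for low back pain. Neither carries a condition that the device is still in place. The synopsis states that reporting is descriptive.

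Subjects from the earlier PRESS registry may be transferred in (Section 10.4). For them the synopsis says: "The above study events will occur for previously enrolled PRESS subjects as applicable (i.e. to be completed study timepoints".

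**The concern.** This is a written data-collection rule, not an omission. It links the end of a subject's participation to removal of the device. The pain endpoints run to 3 years, while an explanted subject leaves within about a month of explant. On the visible text, the later VAS scores are therefore missing by design, for a reason tied to the device itself.

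The study tests no hypothesis, so the reported proportion is the result. If it is an observed-case proportion, its population changes from visit to visit: the share removed through explant can only grow, and is largest at 2 and 3 years. A reader would probably take the figure as the outcome of patients who received the implant, when it would mostly be the outcome of those who still have it. An analysis rule can classify explanted subjects, but it cannot recover scores that were never collected.

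**Working it through.** The plan has no figure to reproduce. The synopsis gives NA for test method and sample size parameters, and the documents give no explant rate or responder rate.

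**Inputs from the documents.** Withdrawal 30 days after explant (Section 9.2). Visit windows from the synopsis: days 45–135, 120–240, 305–425, 670–790 and 1,035–1,155. A cap of 3,000 implanted subjects (Section 9.3), which is a ceiling and not a powered sample size.

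**Assumed inputs.** Let p be the responder rate among subjects still observed, taken as 70%. Let w be the share of implanted subjects explanted and withdrawn before the visit, taken as 2%, 5% or 10%. Let q be the unknown share of those who would meet 20 mm, varied from 0 to 90%. All other subjects are taken as observed.

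**Step 1: which visits are lost.** A visit is certainly lost if the explant day plus 30 falls before its window opens. That means explant before day 15 (3 months), 90 (6 months), 275 (1 year), 640 (2 years) or 1,005 (3 years). Explant at day 60, 180, 365 or 730 ends participation at day 90, 210, 395 or 760 and loses 4, 3, 2 or 1 of the five visits. Explant before day 15 loses all five.

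**Step 2: bounds.** The rate over all implanted subjects, regardless of explant, is p(1−w) + qw. With q between 0 and 1 it lies from p(1−w) to p(1−w) + w, so the width is w whatever p is. The 95% half-width of the observed rate is 1.96 × √(p(1−p)/n), with n = 3,000(1−w).

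| w | Lower: 0.70(1−w) | Upper: lower + w | 95% half-width |
|---|---|---|---|
| 2% | 68.6% | 70.6% | 1.66 points (n = 2,940) |
| 5% | 66.5% | 71.5% | 1.68 points (n = 2,850) |
| 10% | 63.0% | 73.0% | 1.73 points (n = 2,700) |

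The lower bound is also the rate obtained when explant counts as non-response. At 5% explanted the bounds are 47.5–52.5% for p = 50% and 76.0–81.0% for p = 80%.

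**Step 3: observed-case rate minus all-implanted rate.** This is p − [p(1−w) + qw] = w(p−q). At p = 70%, in points:

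| q | w = 2% | w = 5% | w = 10% |
|---|---|---|---|
| 0 | 1.4 | 3.5 | 7.0 |
| 30% | 0.8 | 2.0 | 4.0 |
| 50% | 0.4 | 1.0 | 2.0 |
| 70% | 0 | 0 | 0 |
| 90% | −0.4 | −1.0 | −2.0 |

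**Step 4: against sampling error.** At w = 2% even the worst case, 1.4 points, is below the half-width of 1.66. With 3,000 evaluable subjects (half-width 1.64), the worst-case gap passes the half-width at w = 1.64/0.70 = 2.3%. With 1,500 or 1,000 evaluable subjects (2.32 or 2.84 points) it does so at 3.3% or 4.1%. At q = 30% the three thresholds become 4.1%, 5.8% and 7.1%.

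**Step 5: transferred subjects.** PRESS subjects explanted before transfer may not be in the PRESS 2 data. Suppose half the subjects at a visit are transferred, and the 5% explants in that half all happened before transfer. The pooled non-responder figure is then 0.5 × 66.5 + 0.5 × 70 = 68.25%, not 66.5%. This is why the two groups should be shown separately.

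**Step 6: what later questionnaires would gain.** If a share f of explanted subjects completed the later VAS, the width falls to w(1−f). At f = 70% (assumed), widths of 2, 5 and 10 points become 0.6, 1.5 and 3.0.

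**The case against.** The strongest reply is that the decisive text may be hidden. The End of Study Action Plan is named in Section 9.2 and abbreviated in Section 24.1, but its content is not visible. The schedule tables are redacted, the assessment and statistical sections are not visible, and a sentence fragment after Section 10.4 seems to be the end of a hidden passage on follow-up before withdrawal. A reader might infer that VAS is definitely not collected after explant, or that the plan has no rule on the denominator. Neither is supported. Intent to treat is in the abbreviation list, so such a rule may exist.

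A reader might also infer that the 20 mm rate can only ever be bounded. That holds for one target only: VAS response regardless of explant, over all implanted subjects, without a missing-data model. The visible endpoint does not name that denominator. Counting explant as non-response gives a single number, and describing outcomes while the device is in place is a legitimate aim for a descriptive registry. A model would give a point estimate too, though on assumptions these data could not test.

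Third, the size is entirely assumed. Subjects with a revision or replacement may continue, so only explants followed by withdrawal matter, and ordinary loss to follow-up would leave some uncertainty after any fix. Finally, Section 9.2 already requires every enrolled subject to be accounted for, with withdrawal reasons.

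These points limit the claim but do not remove it. The explant rule is explicit, the permission to follow subjects outside the study names neither VAS nor a schedule, and the endpoints are not restricted to subjects with the device in place. Documenting withdrawals makes the explant count cheap to produce; it does not ensure that the count appears beside the responder rate.

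**Conclusion.** The point holds in limited form. On the visible text, explanted subjects supply no VAS after withdrawal, so an observed-case proportion from 6 months on would largely describe subjects who kept the device. For the rate regardless of explant, the uncertainty equals the explanted share: 5 points at 5% explanted, and within sampling error at about 2% or less near the 3,000 cap. These sizes rest on an assumed 70% observed rate, assumed explant shares and otherwise complete follow-up.

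A reader might conclude that the reported rate will be too high. The documents do not establish that. It is too high only if explanted subjects respond less often than the others. This is plausible, but nothing in the documents shows it, and without later VAS it could not be checked. No hypothesis test is affected. If the End of Study Action Plan already collects VAS at the scheduled visits and allows its analysis, the data-collection part reduces to a clear citation.

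**What to change.** **Reporting.** At each visit, show the cumulative number explanted. Label the observed-case proportion as such. Beside it, give one sensitivity proportion over implanted subjects that counts explanted subjects as non-responders. State the denominator of each, or cite the text that already sets it. Show newly implanted and transferred PRESS subjects separately.

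**Data collection.** In Section 9.2, separate removal of the device from the end of questionnaire collection: explanted subjects who agree complete the remaining VAS, PPR and EQ-5D-5L questionnaires, with no change to their care. If non-visible text already provides this, cite it there. If later questionnaires are not feasible, the reporting change alone would still show the limits.

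**Cost.** One or two extra table rows, a wording change, a consent line and some questionnaire burden; Section 12.2 describes electronic collection at the site, so the burden is not nil. The number of added questionnaires cannot be given: the explant rate is not stated, up to five visits can be lost per subject, and transferred subjects have only their remaining timepoints. Scores after explant may reflect later treatment, so the observed-case proportion should stay beside any figure that uses them.
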